## List of abbreviations

PCI	Percutaneous Coronary Intervention
AMI	Acute Myocardial Infarction
HF	Heart Failure
STEMI	ST-Segment Elevation Myocardial Infarction
RAAS	Renin-Angiotensin-Aldosterone System
CABG	Coronary Artery Bypass Graft
ACEI	Angiotensin-Converting Enzyme Inhibitors
ARB	Angiotensin Receptor Blocker
SBP	Systolic Blood Pressure
AUC	Area Under Curve
ANP	Atrial Natriuretic Peptide
BNP	Brain Natriuretic Peptide
cGMP	Cyclic Guanosine Monophosphate
HTN	Hypertension
eGFR	Estimated Glomerular Filtration Rate
MDRD	Modification of Diet in Renal Disease
AST	Aspartate Aminotransferase
ALT	Alanine Aminotransferase
ULN	Upper Limit of Normal
hCG	Human Chorionic Gonadotropin
FSH	Follicle-Stimulating Hormone
Bid	Bis In Die
ARNI	Angiotensin Receptor Neprilysin Inhibitor
CCB	Calcium Channel Blockers
AM	Ante Meridiem
PM	Post Meridiem
MRA	Mineralocorticoid Receptor Antagonist
CV	Cardiovascular
AEs	Adverse Event(s)
SAEs	Serious Adverse Event(s)
LVEDV	Left Ventricular End-Diastolic Volumes
LVESV	Left Ventricular End-Systolic Volumes
LVEF	Left Ventricular Ejection Fraction
BUN	Blood Urea Nitrogen
LDL	Low Density Lipoprotein
HDL	High Density Lipoprotein
Hs-cTnI	High Sensitivity Cardiac Troponin I
ECG	Electrocardiogram
NEP	Neutral Endopeptidase

DMC	Data Monitoring Committee
eCRFs	Electronic Case Report Form(s)
BMI	Body Mass Index
FAS	Full Analysis Set
REB	Research Ethics Board

## Glossary of terms

Assessment	A procedure used to generate data required by the study
Enrollment	Point/time of patient entry into the study; the point at which informed consent must be obtained (i.e. prior to starting any of the procedures described in the protocol)
Investigational drug	The study drug whose properties are being tested in the study
Patient number	A number assigned to each patient who enrolls in the study. When combined with the center number, a unique identifier is created for each patient in the study.
Period	A major subdivision of the study timeline; begins and ends with major study milestones such as enrollment, randomization, completion of treatment, etc.
Premature patient withdrawal	Point/time when the patient exits from the study prior to the planned completion of all study drug administration and assessments; at this time all study drug administration is discontinued and no further assessments are planned
Randomization number	A unique identifier assigned to each randomized patient, corresponding to a specific treatment arm assignment
Stop study participation	Point/time at which the patient came in for a final evaluation visit or when study drug was discontinued whichever is later
Study drug	Any drug administered to the patient as part of the required study procedures; includes investigational drug and any control drugs
Study drug discontinuation	Point/time when patient permanently stops taking study drug for any reason; may or may not also be the point/time of premature patient withdrawal
Variable	Information used in the data analysis; derived directly or indirectly from data collected using specified assessments at specified timepoints

## Protocol synopsis

**Protocol title:** Angiotensin receptor-neprilysin inhibitor (ARNI, Sacubitril/Valsartan) versus Enalapril in patients with acute anterior wall ST-elevation myocardial infarction after emergency PCI: a prospective randomized trial

**Rationale & background information:** Ventricular remodeling after acute myocardial infarction (AMI) is closely related to the occurrence of heart failure (HF). Despite opening the infarct-related artery as early as possible and using the best medical treatment, about 41.5% of STEMI patients still have ventricular remodeling at 6 months. LV remodeling is a complex pathophysiological process that develops gradually over time. Neuroendocrine hormones, persistently activated, play an important role in this process, except for the extent of initial myocardial injury, and are closely associated with the progression of heart failure (HF).

In recent years, the application of Sacubitril/Valsartan (Sac/Val) has brought bright sight to patients with heart failure. Sac/Val can inhibit the activation of endorphinase and renin-angiotensin-aldosterone system (RAAS) at the same time. According to PARADIGM-HF study and other researches, Sac/Val could reduce cardiovascular mortality and re-admission rate of heart failure patients who had a reduced heart ejection fraction. Whether the initiation of Sac/Val immediately is effective and safe among patients with acute anterior STEMI (a high-risk factor for HF) is unknown. Therefore, the purpose of this study is to evaluate the safety and effectiveness of immediate initiation of Sac/Val in patients with acute anterior STEMI after PCI.

### Objectives:

#### Primary objective:

The primary objective of this study is to test if Sac/Val is superior to enalapril in reducing the concentration of NT-proBNP and improving the main cardiac ultrasound parameters in patients with acute anterior STEMI after PCI.

#### Secondary objective:

The Secondary objective of this study is to test if Sac/Val is superior to enalapril in reducing the incidence of cardiovascular events (a composite of death, reinfarction, outpatient HF or HF hospitalization, arrhythmia, and stroke).

### Population

#### Inclusion criteria

Patients eligible for inclusion in this study have to fulfill all of the following criteria:

1. Patients must give written informed consent before any assessment is performed
2. Outpatients  $\geq 18$  years of age, male or female
3. Had typical pain and Diagnosed as acute anterior STEMI according to electrocardiogram, high-sensitivity troponin, and coronary angiography

4. Systolic blood pressure  $\geq 100$ mmHg without symptoms of dizziness during the last 12 hours prior to randomization

**Exclusion criteria**

1. Previous history of myocardial infarction or chronic heart failure
2. Previous PCI, coronary artery bypass graft (CABG), implantation of other heart assist devices or heart transplantation
3. Known history of angioedema
4. Previous history of intolerance to recommended target doses of ACEIs or ARBs.
5. Previous use of sacubitril/valsartan
6. History of hypersensitivity or contraindications to the study drugs including ACEI, ARB, sacubitril/valsartan
7. Symptomatic hypotension and/or a SBP  $< 100$  mmHg at Visit 1 (screening), Visit 2 (randomization), Visit 3 (outpatient dose titration) or Visit 4 (follow-up)
8. Estimated GFR  $< 30$  mL/min/1.73m^2 as measured by the simplified MDRD formula at Visit 1 (screening), Visit 2 (randomization), Visit 3 (outpatient dose titration) or Visit 4 (follow-up) or  $> 25\%$  decline in eGFR between Visit 1 and Visit 2 or between Visit 2 and Visit 3 or between Visit 3 and Visit 4
10. Serum potassium  $> 5.2$  mmol/L at Visit 1 (screening), Visit 2 (randomization), Visit 3 (outpatient dose titration) or Visit 4 (follow-up)
11. History of severe pulmonary disease
12. Diagnosis of peripartum or chemotherapy induced cardiomyopathy prior to Visit 1
13. Documented untreated ventricular arrhythmia with syncopal episodes within the 3 months prior to Visit 1
14. Symptomatic bradycardia or second or third degree heart block without a pacemaker
15. Presence of hemodynamically significant mitral and/or aortic valve disease, except mitral regurgitation secondary to left ventricular dilatation
16. Presence of other hemodynamically significant obstructive lesions of left ventricular outflow tract, including aortic and sub-aortic stenosis
17. Life expectancy is less than 1 year
18. Any surgical or medical condition which might significantly alter the absorption, distribution, metabolism, or excretion of study drugs, including but not limited to any of the following
  - History of active inflammatory bowel disease during the 12 months before Visit 1.
  - Current duodenal or gastric ulcers during the 3 months prior to Visit 1
  - Evidence of hepatic disease as determined by any one of the following: AST or ALT values exceeding 2 x ULN at Visit 1, history of hepatic encephalopathy, history of esophageal varices, or history of portacaval shunt
  - Active treatment with cholestyramine or colestipol resins
19. Pregnant or nursing (lactating) women, where pregnancy is defined as the state of a female after conception and until the termination of gestation, confirmed by a positive hCG laboratory test ( $> 5$  mIU/mL)
20. Women of child-bearing potential, defined as all women physiologically capable of becoming pregnant, including women whose career, lifestyle, or sexual orientation precludes intercourse with a male partner and women whose partners have been

sterilized by vasectomy or other means, UNLESS they are using two birth control methods. The two methods can be a double barrier method (if accepted by the local regulatory authority and ethics committee) or a barrier method plus a hormonal method

• Adequate barrier methods of contraception include: diaphragm, condom (by the partner), intrauterine device (copper or hormonal), sponge or spermicide. Hormonal contraceptives include any marketed contraceptive agent that includes an estrogen and/or a progesterone agent.

• Reliable contraception should be maintained throughout the study and for 7 days after study drug discontinuation.

• Women are considered post-menopausal and not of child bearing potential if they have had 12 months of natural (spontaneous) amenorrhea with an appropriate clinical profile (e.g. age appropriate, history of vasomotor symptoms) or six months of spontaneous amenorrhea with serum FSH levels > 40 mIU/mL or have had surgical bilateral oophorectomy (with or without hysterectomy) at least six weeks ago. In the case of oophorectomy alone, only when the reproductive status of the woman has been confirmed by follow up hormone level assessment.

### **Investigational drugs**

#### **after PCI**

The following study drugs will be provided:

- Enalapril 2.5 mg tablets
- Enalapril 5 mg tablets
- Enalapril 10 mg tablets

#### **Randomization, Outpatient dose titration and follow-up**

All eligible patients will be randomized to receive either Sac/Val or enalapril in addition to optimal AMI therapy, as considered appropriate by the investigator and in accordance with standard therapy guidelines, but with the exception of an ACEI or ARB as this will be replaced by study drug. The use of an ACEI or an ARB in addition to study drug after randomization is strictly prohibited.

The following study drugs will be provided:

- Enalapril 2.5 mg tablets (enalapril dose level 1)
- Sacubitril/Valsartan 50 mg tablets (Sacubitril/Valsartan dose level 1, Sacubitril/Valsartan to match enalapril 2.5 mg film-coated tablets)
- Enalapril 5 mg tablets (enalapril dose level 2)
- Sacubitril/Valsartan 100 mg tablets (Sacubitril/Valsartan dose level 2, Sacubitril/Valsartan to match enalapril 5 mg film-coated tablets)
- Enalapril 10 mg tablets (enalapril dose level 3)
- Sacubitril/Valsartan 200 mg tablets (Sacubitril/Valsartan dose level 3, Sacubitril/Valsartan to match enalapril 10 mg film-coated tablets)

Target doses: Sacubitril/Valsartan 200 mg bid and enalapril 10 mg bid.

## **Study design**

This study is a single-center, prospective, double-blind, randomized, parallel-group, two-arm, short-term trial to compare Sacubitril/Valsartan 200 mg bid to enalapril 10 mg bid in concentration of NT-proBNP reduction and main cardiac ultrasound parameters improvement in patients with acute anterior STEMI after PCI.

## **Duration of the study**

As planned, it is expected to be up to 18 months: a recruitment period of approximately 12 months and a minimal follow-up of 6 months.

## **Study visits**

### **Screening**

#### **Visit 1 (Screening Visit)**

All patients must provide informed consent before any study-specific procedure is performed. At Visit 1, patients' eligibility for entering the randomization period, including whether the patient's vital signs are stable after PCI, will be assessed by the investigator. Whether enalapril is included in the medicine used immediately after the operation. Screening potassium levels and eGFR will be assessed by sending blood samples to the central laboratory and only patients with the required values per the entry criteria will be eligible for entering the randomization period, which will begin at Visit 2.

### **Randomization**

#### **Visit 2 (Randomization Visit)**

Patients who have met all the inclusion criteria and none of the exclusion criteria at the end of the screening period will be randomized to either enalapril or Sacubitril/Valsartan in a 1:1 ratio. Patients randomized to enalapril continue to receive enalapril, while patients randomized to sacubitril/valsartan discontinue enalapril to ensure a minimum 36-hour washout period prior to initiation of ARNi therapy. The first dose of sacubitril/valsartan is followed by 6 hours of monitoring for hypotension. After the condition is stable, patients can be discharged from the hospital at any point in time at the discretion of the clinician-investigator. The starting dose during the in-hospital initiation phase is selected using a dose titration algorithm based on systolic blood pressure (SBP) (**Figure 1**).

[figure not shown]

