## **4 Study design**

This study is a single-center, prospective, randomized, double-blind, parallel-group, two-arm, short-term trial to compare sacubitril/valsartan 200 mg bid to enalapril 10 mg bid in concentration of NT-proBNP reduction and main cardiac ultrasound parameters improvement in patients with acute anterior STEMI after PCI.

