### **4.2.2 Randomization**

#### **Visit 2 (Randomization Visit)**

Patients who have met all the inclusion criteria and none of the exclusion criteria at the end of the screening period will be randomized to either enalapril or sacubitril/valsartan in a 1:1 ratio. Patients randomized to enalapril continue to receive enalapril, while

patients randomized to sacubitril/valsartan discontinue enalapril to ensure a minimum 36-hour washout period prior to initiation of ARNi therapy. The first dose of sacubitril/valsartan is followed by 6 hours of monitoring for hypotension. After the condition is stable, patients can be discharged from the hospital at any point in time at the discretion of the clinician-investigator. The starting dose during the in-hospital initiation phase is selected using a dose titration algorithm based on systolic blood pressure (SBP) (Figure 1).

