#### **4.2.3 Outpatient dose titration period**

##### **Visit 3 (Outpatient dose titration period Visit)**

During the outpatient dose titration phase, patients continue to receive sacubitril/valsartan or enalapril. There are 3 available doses of study drug administered twice daily. All subsequent dose changes during the medication titration period is selected using a dose titration algorithm based on systolic blood pressure (SBP) (Figure 1). Clinician-investigators are encouraged to up titrate sacubitril/valsartan to target dose (i.e., dose level 3) as tolerated during the medication titration phase. every attempt should be made to complete the dose titration period within 8 weeks regardless of any down-titration that may occur.

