## **7 Visit schedule and assessments**

All patients, including those who discontinue the study medication before completing the study, should continue attending the scheduled visits as outlined in Table 7-1 until the study ends. At that point all patients will return to the study sites as soon as possible to undergo the end of study visit assessments. If any patient refuses to return for these assessments or is unable to do so, every effort should be made to contact him/her or a knowledgeable informant by telephone to ask if any of the secondary and safety endpoints have occurred at the foreseen visit dates for the remaining duration of the study. Documentation of attempts to contact the patient should be recorded in the patient's record.

All data obtained from the assessments listed in Table 7-1 and described in detail in the subsections below must be supported in the patient's source documentation (e.g., medical charts or patient notes).

Table 7-1 indicates which data remain in source documents only (S), or may be entered directly into the database (D; i.e., these data are considered source documentation and do not require separate source documentation), or are entered into the database from separate source documents (DS). Assessments that generate data for database entry and are recorded on electronic case report forms are listed using the electronic case report form name. Assessments that are transferred to the database electronically (e.g., laboratory data) are listed by test name.

There is a short washout periods (approximately 36 hours for each) during the randomization period to minimize the potential risk of angioedema due to overlapping ACE-NEP inhibition at Visit 2 (Section 7.5.7): after randomization at Visit 2.

For example, if a patient's Visit 2 is on Wednesday, he/she must not take any doses of the enalapril medication after the Tuesday evening dose. The patient will then start to take the first dose of the sacubitril/valsartan medication on Thursday morning.

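### The trial is labelled double-blind, but the one-arm enalapril stop and first-dose monitoring at Visit 2 let patients on enalapril and their treating staff infer the arm

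*Protocol*

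**What the plan says.** Section 4 states: "This study is a single-center, prospective, randomized, double-blind, parallel-group, two-arm, short-term trial". The synopsis has the same label ("This study is a single-center, prospective, double-blind, randomized, parallel-group, two-arm, short-term trial"), and Section 1 repeats it.

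The Visit 2 text, in the synopsis and again in 4.2.2, separates the arms by procedure: "Patients randomized to enalapril continue to receive enalapril, while patients randomized to sacubitril/valsartan discontinue enalapril". The stop is there "to ensure a minimum 36-hour washout period prior to initiation of ARNi therapy". It goes on: "The first dose of sacubitril/valsartan is followed by 6 hours of monitoring for hypotension". No comparable pause or observation is stated for the enalapril arm.

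Section 7 gives a worked example with Visit 2 on a Wednesday: "he/she must not take any doses of the enalapril medication after the Tuesday evening dose". Then: "The patient will then start to take the first dose of the sacubitril/valsartan medication on Thursday morning".

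For Visit 3, the synopsis and 4.2.3 say: "Clinician-investigators are encouraged to up titrate sacubitril/valsartan to target dose (i.e., dose level 3". One sentence in 6.4.3 likewise describes down-titration of sacubitril/valsartan by name.

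The only masking device described is in 6.1 and the synopsis: at each of three dose levels the sacubitril/valsartan tablet is made to match the enalapril tablet.

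**The concern.** A double-blind label tells the reader that neither the patient nor the staff who treat and assess the patient can tell the arm. Here the allocated arm determines whether the patient stops a drug for a day and a half and is then observed for six hours. Anyone at the bedside can see that.

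Several outcomes and decisions in this trial depend on judgement:

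- LVEF, LVEDV and LVESV are primary outcomes traced by the biplane Simpson method (7.4.5).
- Dose changes and background-drug changes are left largely to the investigator (6.4.3, 6.4.5).
- Outpatient heart failure, part of the secondary composite, requires a visit for that diagnosis and a decision to start or intensify treatment (7.4.3).

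The protocol does not say that echo readers or adjudicators are kept unaware of the arm. The bare label is therefore the only stated protection, and the Visit 2 procedure removes it for treating staff.

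**Working it through.** **1. What each arm experiences from Visit 2 (synopsis, 4.2.2)**

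| Step | Enalapril arm | Sacubitril/valsartan arm |
|---|---|---|
| Enalapril | goes on | stops |
| Interval before randomized drug | none stated | at least 36 h |
| Monitoring after first dose | none stated | 6 h |

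**2. How visible the gap is.** Section 6.4.2 sets dosing at about 08:00 and 19:00. I assume the same times for enalapril before Visit 2. In the Section 7 example:

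- Tuesday 19:00 to midnight = 5 h; Wednesday = 24 h; midnight to Thursday 08:00 = 8 h.
- Total = 5 + 24 + 8 = 37 h, which meets the 36-hour minimum.
- Doses left out: Wednesday 08:00 and Wednesday 19:00, so two.

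On this schedule, omitting a single dose always leaves 11 + 13 = 24 h, short of 36 h. Any interval that meets the minimum therefore omits at least two scheduled doses.

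**3. Whether anything conceals it.** Matching tablets mask which tablet is taken, not whether one is taken. I looked for placebo or dummy doses during the gap, equivalent observation in the enalapril arm, or a separate unblinded drug handler. None is described. Section 8.1 mentions placebo only in a generic definition of study drug, and the table of contents has no section on blinding.

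**4. Washout timing.** 4.2.2 applies the stop to one arm, once randomized. Section 7 also places the washout after randomization at Visit 2, but its example makes the evening before Visit 2 the last enalapril dose, when the arm is not yet known. Section 7 further gives the length as about 36 hours for each, without saying what is counted. These statements do not describe one procedure.

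**5. Titration wording.** 4.2.3 and one sentence in 6.4.3 name sacubitril/valsartan. The rest of 6.4.3 takes study drug in either arm to dose level 3, and 6.1 gives both arms a target dose. This is an inconsistency of wording in the Visit 3 period.

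**6. Who is affected.** Section 10.6 plans 142 patients. Visit 1 treats use of enalapril after the procedure as something to be checked, although 6.1 supplies enalapril after PCI. The number on enalapril at Visit 2 is not given, so 142 is an upper bound. For a patient not on enalapril, only the monitoring difference would remain.

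**The case against.** The best defence is that much of the machinery of a blind exists. Tablets match at paired dose levels, packs are supplied by arm and level, a separate researcher holds the allocation, NT-proBNP goes to a central laboratory, and events go to an adjudication committee. The phrase in Section 7 about 36 hours for each might mean that both arms pause. The first part stands: nothing in the tablets themselves need reveal the arm after the first dose. It does not cover the gap before that dose. The reading that both arms pause fails because 4.2.2 says plainly that the enalapril arm continues.

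Four stronger readings are tempting, and the documents do not support them:

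- **Only one arm is pushed to target, so the dose comparison is unequal.** 6.4.3 and 4.2.4 ask for the target or maximal tolerated dose of study drug in both arms. Because levels are paired, a blinded investigator could still titrate by level. The drug-named sentences apply to Visit 3, so they cannot reveal the arm at Visit 2.
- **The washout could shrink to 24 hours.** Wednesday 08:00 to Thursday 08:00 is 24 h, but that sequence breaks both the Section 7 example and the 36-hour minimum in 4.2.2.
- **The error rate rises to about 16–29%.** With 64 per group and SD 6 (10.6), SE = 6 × √(2/64) = 1.06. An assumed shift of 1.0 to 1.5 LVEF points would give that range for a two-sided 5% test. The arithmetic is right, but the shift has no source in the protocol and presupposes echo readers who know the arm.
- **Everyone knows the arm.** The inference holds for patients on enalapril and their treating staff. For echo readers, laboratory and adjudicators the protocol is silent, so for them it is a risk.

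**Conclusion.** The contradiction is in the text and needs no assumption: the protocol claims a double blind and prescribes a visible one-arm procedure at the point of allocation. That patients on prior enalapril and their treating staff can infer the arm follows from the lack of any described dummy dosing or equivalent monitoring. The visible difference is at least 36 hours (37 in the protocol's own example, with two doses omitted) plus six hours of observation, in at most 142 patients. The resulting bias in echo measures, titration, background treatment and outpatient heart failure reporting cannot be sized from the documents. The washout timing and titration wording are lesser inconsistencies that need correcting with it. This must be fixed: a label can be reworded later, but a patient who has passed through Visit 2 cannot be blinded again.

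**What to change.** Reconcile Sections 4, 4.2.2 and 7 (and the matching synopsis and Section 1 text) in one of two ways:

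- **Keep the label.** State how the blind is maintained through washout, first dose and monitoring. The clinical sequence is for the clinical team to settle.
- **Change the label.** Drop double-blind and describe the trial as open-label with blinded outcome assessment. Have echo recordings, NT-proBNP samples and adjudication packages handled under patient number without the arm, and say so in 7.4.2, 7.4.4 and 7.4.5.

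In either case, word the titration text in 4.2.3 and 6.4.3 by study drug and dose level for both arms. Reconcile the washout timing in 4.2.2 and 7, including whether it starts before or after randomization and to whom it applies.

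The cost is a wording amendment. Changing the label also means a weaker but true description of the design and some masking work on outcome data that are collected anyway.
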